7.2.3.4 Follow-up in the Event of a Pregnancy

If a female subject, or the female partner of a male subject, who has received IMP becomes pregnant, the pregnancy will be recorded. The ethics committee and the Sponsor will be informed. The subject will be asked to provide information on the outcome of the pregnancy, including premature termination should the case arise.

Spontaneous miscarriage and congenital abnormalities will be reported as SAEs.

The follow-up period will be deemed to have ended when the health status of the child has been determined at birth.

7.2.4 Subject Withdrawals

The Principal Investigator will make every reasonable attempt to complete the study. A subject may withdraw for any reason. The Principal Investigator will advise the Sponsor of the withdrawal of any subject.

A subject may be withdrawn in any of the following circumstances:

- AEs;
- Protocol violation;
- Withdrawal of consent;
- Termination of the study by the Principal Investigator or Sponsor.

Subjects who voluntarily withdraw are termed dropouts. Dropouts and subjects withdrawn due to protocol violations may be replaced following discussion with the Principal Investigator and Sponsor.

Subjects withdrawn due to an adverse event will not be replaced.

Should a subject request or decide to withdraw from the study, all efforts must be made to complete and report the observations as thoroughly as possible up to the date of withdrawal. Subjects withdrawing due to an AE should be followed up according to follow-up visit.

7.2.5 Study Termination

The Sponsor has the right to terminate this study at any time. Reasons for terminating the study may include, but are not limited to, the incidence or severity of adverse events in this or other studies indicating a potential health hazard to subjects.

8.0 STUDY TREATMENT

8.1 Investigational Product(s)

GBT440 oral capsules 300 mg capsules.

8.1.1 Supply, Packaging and Labelling

GBT440 oral capsules will be supplied to the Investigational Site by GBT or their representative.

Individual subject treatments will be dispensed by the Investigational Site Pharmacist.

A release document signed by Investigational Site Pharmacist or designee at the Investigational Site will be placed in the appropriate section of the Trial Master File to document labelling and dispensing of the study drug to the subject. A Pharmacy Manual (detailing IMP handling instructions) will be in place to cover all pharmacy related activities, and IMP accountability. .

8.1.2 Storage and Handling Procedures

All study medication will be stored at 25°C protected from light in the storage area of the Investigational Site Pharmacy, which is a secure, temperature controlled, locked environment with restricted access.

No special procedures for the safe handling of GBT440 are required. The Sponsor will be permitted upon request to audit the supplies, storage, dispensing procedures and records provided that the blind of the study is not compromised.

8.1.3 Accountability

In accordance with GCP, the Investigational Site will account for all supplies of GBT440. Details of receipt, storage, assembly and return will be recorded.

All unused supplies of GBT440 will either be destroyed by the Investigational Site or returned to the study Sponsor at the end of the study in accordance with instruction by the Sponsor.

8.2 Dosage and Administration

GBT440 will be administered as oral capsule formulations with water as follows.

During the outpatient dosing period and in between study visits, subjects will not be required to fast and should take their study drug in the morning.

On study visits during the dosing period when PK samples are collected, subjects should have an overnight fast prior to taking study drug in clinic.

Additionally, during the outpatient dosing period in between study visits, subjects may be contacted weekly phone by clinic staff to confirm study drug administration.

Dosing will be stopped if the Hb is >12.8 g/dL but may restart at a reduced dose once the Hb is <12 g/dL following consultation and agreement of the referring SCD NHS haematologist.

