5.3 Rationale

To date GBT440 has been generally well tolerated in patients with SCD for up to 90 days. There have not been any drug related SAEs and no unexpected AEs.

In addition preliminary pharmacodynamic data from patients with SCD treated with GBT440 for 28 days indicate a significant reduction in the number of the sickled RBCs, improvement in haemolysis markers as evidenced by declines in reticulocyte counts, unconjugated bilirubin and lactate dehydrogenase (LDH) levels and an improvement in anemia are encouraging. The initial impression of blinded data reviewed by the SMC suggests emerging data from GBT440-001 suggest that these improvements are sustained over 90 days of treatment.

Given the significant unmet need in SCD, there is an interest in determining the potential for further development of GBT440 by generating safety and efficacy data with longer term dosing (greater than 90 days) as quickly as possible while still safeguarding the safety of subjects. To do this safely and efficiently subjects in ongoing cohorts 17 and 15 in the GBT440-001 study will be enrolled in this proposed extension study. Additionally, SCD subjects from earlier Cohorts (i.e. Cohorts 7, 11, 12, 14 or 16) from GBT440-001 will be approached for enrollment into this study. Because of delays in initiating the GBT440-024 study, several subjects from Cohort 17 of GBT440-001 completed dosing and were unable to participate in this study. Many subjects from earlier cohorts expressed interest in longer term dosing with GBT440. The inclusion criteria have been expanded to allow enrolment of subjects with SCD who have completed the GBT440-001 study however total enrollment into this study will be limited to a total of 16 subjects. To continue to ensure the safety of subjects, regular safety monitoring and additional periodic SMC review during the total 6 month treatment period will be implemented. In particular, haemoglobin levels, reticulocyte count and erythropoietin levels will be monitored for evidence of tissue hypoxia/hyperviscosity. GBT440 treatment will be discontinued for excessive Hb increase or dose reduced for evidence of hyperviscosity based on increasing Hb, erythropoietin and reticulocyte levels.

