5.3.1 Rationale for Dose Titration

Dose titration has been added because data from the GBT440-001 study has shown a linear and highly significant relationship between GBT440 blood level and improvement in hemolysis and no plateau effect has been reached. This suggests that subjects may derive greater benefit at higher doses achieving higher haemoglobin occupancy. Furthermore the target for optimal efficacy based on individuals with HbS/Hereditary persistence of fetal haemoglobin is 20-30% haemoglobin occupancy (Ngo 2011) and the preliminary PK data from Cohort 17 showed that the majority of subjects did not maintain haemoglobin occupancy >20% at 900 mg daily dosing. In addition, no dose limiting toxicities or concerning dose-or exposure related toxicities pose a safety concern with higher doses. Doses of 1000 mg for 28 days and 900 mg for 90 days have been well tolerated, with the majority of AEs were Grade 1 or 2 in severity. At 1500 mg, the predicted C_{max} is 167 μ g/mL, which is less than the C_{max} already observed and found to be well-tolerated in healthy volunteers in GBT440-001 (294 μ g/mL at 900 mg [Cohort 10]).

To assess the higher dose of 1500 mg, subjects will be dose escalated by 300 mg over 2-week intervals. The principal investigator will determine if the 600 mg or the 900 mg dose is well tolerated (after at least 28 days of prior dosing), and that the subject may receive further benefit from higher dosing (further improvement in haemoglobin, reticulocyte count or unconjugated bilirubin) the dose may be increased by one capsule (300 mg) every two weeks up to a maximum of 1500 mg.

This study will be performed in compliance with the protocol, ICH GCP and applicable regulatory requirements. Aspects of the study concerned with the investigational medicinal product(s) (IMPs) will meet the requirements of EU GMP.

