7	07001-07008		2407-1001 to 2407-1008
11	11001-11016		2411-1001 to 2411-1016
12	12001-12014		2412-1001 to 2412-1014
14	14001-14008		2414-1001 to 2414-1008
16	16001-16008		2416-1001 to 2416-1008

If a subject from GBT440-001 elects not to participate in this protocol, their corresponding identification number would remain unused.

All Subjects will receive a total of 6 months treatment with GBT440 which will include treatment with GBT440 in the GBT440-001 study for subjects in Cohort 15 or 17. Subjects from Cohort 7, 11, 12, 14, 16 or 17 who received either GBT440 or placebo will receive a total of 6 months of treatment with GBT440 in this study.

A Safety Monitoring Committee (SMC) consisting of the Principal Investigator, Sponsor Medical Monitor, and Independent Safety Physician will have overall responsibility for assessing safety and tolerability. The SMC will review cumulative data at least monthly to determine whether continued dosing may proceed. The responsibilities of the SMC will be described in a separate charter.

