8.2.1 Dose Titration

Provided the Principal Investigator determines that the 600mg dose (in Cohort 15), 900 mg dose (in Cohort 17), and 900 mg dose in the Cohorts 7, 11, 12, 14, 16 or 17 is well tolerated (after at least 28 days of dosing), and that the subject may receive further benefit from higher dosing (further improvement in haemoglobin, reticulocyte count or unconjugated bilirubin) the dose may be increased by one capsule (300 mg) every two weeks up to a maximum of 1500 mg dose.

When increasing the dose, the subject should return to clinical every 2 weeks for Laboratory and AE assessments

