9.0 STUDY PROCEDURES

Table 2 Estimated Blood Volumes:

Assessment	Sample Volume (mL)	No. of Samples	Total Volume (mL)
Sickle Cell Disease Subjects: Multiple Dose			
Safety			
Serum Biochemistry	3.5	Up to 10	35.0
Coagulation	1.8	Up to 8	14.4
Haematology	2.0	Up to 10	20.0
Pregnancy	3.5	8	28.0
Hba1c	3.5	7	24.5
Pharmacokinetic			
GBT440	2.0	11	22.0
Pharmacodynamic			
Serum erythropoietin (EPO)	3.5	Up to 8	28.0

Assessment		Sample Volume (mL)	No. of Samples	Total Volume (mL)
	Frozen Plasma Reserved for immunology/inflammation and exploratory markers	5.0	Up to 8	40.0
	Haemoglobin electrophoresis	2.0	Up to 4	8.0
	Carboxyhaemoglobin	2.0	Up to 7	14.0
Disease Related				
	Dense Cells	2.0	Up to 8	16.0
	NT pro-BNP	2.0	Up to 8	16.0
Total [b]				335.9

Sample volumes are based on direct venipuncture.

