- f: PK samples will be drawn pre dose. If the dose is increased to 1500 mg, please collect the following timepoints: pre dose, then 1-4 hours, 6-8 hours and 24 hours post dose on study visit days of Day 15 (± 3 days), Day 60 (± 3 days) and Days 90 (± 3 days) of receiving 1500 mg.g: Days 15 and 45 are only to be conducted if the dose is increased to 1500 mg.
- h: Can be omitted if measurements were collected in the past 7 days as part of the GBT440-001 study.

Table 5 Schedule of Assessments for Groups 2, 4 and 5

Groups 2: Subjects from Cohort 17 in the GBT440-001 study who have received placebo for 4 months will receive GBT440 900mg per day for 6 months

Group 4: Subjects from Cohort 15 in the GBT440-001 study who have received placebo for 2 months will receive GBT440 900 mg per day for 6 months

Group 5: Subjects with SCD from Cohorts 7, 11, 12, 14, 16 or 17 in the GBT440-001 study will receive GBT440 900 mg per day for 6 months

Assessments	Enrolment a	Baseline for Cohort 7,11,12,14, 16 or 17 (within 7 days of Day 1)	Outpatient Treatment Period											
			1 +/-3 days a	15 +/-3 days	30 +/-3 days	45 +/-3 days	60 +/-3 days	90 +/-3 days	120+/-3 days	150+/-3 days	180 +/-3 days	187+/-3 days	194 +/-5 days	208 End
Day number	Last treatment day GBT440-001 (+6 days) Cohorts 15 and 17													
Visit number	0		1	2	3	4	5	6	7	8	9	10	11	12
Informed consent	X	X												
Eligibility assessment	X	X												
Medical History	X	X												
Physical examination b	X	X		X	X		X	X	X	X	X			X
Weight	X	X		X	X	X	X	X	X	X	X			X
Vital signs	X	X	X	X	X	X	X	X	X	X	X			X
12 Lead ECG (single) c	X	X			X		X	X	X	X	X			
Drug administration d				X-----							X			
Adverse events				X-----										X
Urinalysis e	X	X						X	X	X	X			X
Urine microalbumin/creatinine	X	X						X			X			
Haematology e	X	X		X	X	X	-	X	X	X	X			X
Serum biochemistry e	X	X		X	X	X	X	X	X	X	X			X
Coagulation e	X	X		X		X		X	X	X	X			X
Pregnancy test (females only)	X	X			X		X	X	X	X	X			X
Haemoglobin electrophoresis		X						X			X			X
PK samples (plasma and whole blood) f	X			X	X		X	X	X	X	X	X	X	X
Serum erythropoietin	X ^h	X			X		X	X	X	X	X			X
Exploratory plasma biomarkers	X ^h	X			X		X	X	X	X	X			X

Assessments	Enrolment a		Outpatient Treatment Period											
			1 +/-3 days	15 +/-3 days	30 +/-3 days	45 +/-3 days	60 +/-3 days	90 +/-3 days	120+/-3 days	150+/-3 days	180 +/-3 days	187+/-3 days	194 +/-5 days	208 End

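### In Groups 2, 4 and 5, subjects not being up-titrated have no scheduled haemoglobin test from Day 45 to Day 90, although the 12.8 g/dL dosing stop relies on the schedule

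*Combined protocol and SAP*

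**What the plan says.** Section 8.2 states: "Dosing will be stopped if the Hb is >12.8 g/dL but may restart at a reduced dose once the Hb is <12 g/dL", with restart subject to agreement from the referring haematologist. No testing frequency is attached to either threshold.

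Section 5.3 describes a joint watch: "haemoglobin levels, reticulocyte count and erythropoietin levels will be monitored for evidence of tissue hypoxia/hyperviscosity". Table 3 places haemoglobin and reticulocyte count in the haematology panel, and LDH and bilirubin in serum biochemistry.

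Table 5 in Section 17.0 covers Groups 2, 4 and 5. With blank cells closed up, its haematology row reads "Haematology e X X X X X - X X X X X" and its biochemistry row reads "Serum biochemistry e X X X X X X X X X X X". The two rows differ only at Day 60. Footnote e, attached to both, allows extra samples if clinically indicated.

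Section 8.2.1 adds visits for subjects being titrated: "When increasing the dose, the subject should return to clinical every 2 weeks for Laboratory and AE assessments". Section 7.1 says of the Safety Monitoring Committee: "The SMC will review cumulative data at least monthly to determine whether continued dosing may proceed".

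**The concern.** A mandatory stop at a laboratory value works only if the value is measured. Rising haemoglobin is the expected effect of the drug, and Section 5.3 says treatment will be discontinued if the rise is excessive. A site that follows Table 5 exactly would have no scheduled result able to trigger the stop in a constant-dose subject between Day 45 and Day 90.

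Three things follow for such a subject:

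- At Day 60 only erythropoietin, of the three markers in Section 5.3, is scheduled. It would have to be read without the haemoglobin and reticulocyte values meant to accompany it.
- A monthly committee review falling in the gap could have no new scheduled haemoglobin on which to judge continued dosing.
- Haemoglobin and reticulocytes, both haemolysis markers in Section 9.2.1, have no scheduled Day 60 value, while LDH, bilirubin and PK do.

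**Working it through.** There is no power or sample-size figure to reproduce here. The check is a reading of the schedule and some date arithmetic.

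**Alignment of the row.** Table 5 has 14 columns: Enrolment, Baseline, and Days 1, 15, 30, 45, 60, 90, 120, 150, 180, 187, 194 and 208. The haematology row has 14 cells, so each cell maps to one column. The marks fall at Enrolment, Baseline and Days 15, 30, 45, 90, 120, 150, 180 and 208. The dash falls at Day 60, and Days 1, 187 and 194 are blank. The biochemistry row also has 14 cells and has a mark at Day 60.

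**Other sources of haemoglobin at Day 60.** Biochemistry, erythropoietin, dense cells and PK are drawn, but none is the panel that reports haemoglobin or reticulocytes. Haemoglobin electrophoresis is not scheduled that day. Table 6 (Group 3) does schedule haematology at Day 60.

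**Gaps between scheduled on-treatment tests.** Each visit carries a window of 3 days either way, so a nominal gap can shrink or stretch by 6 days.

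| Interval | Nominal gap (days) | With windows |
|---|---|---|
| Day 15 to 30 | 15 | 9 to 21 |
| Day 30 to 45 | 15 | 9 to 21 |
| Day 45 to 90 | 45 | 87 − 48 = 39 to 93 − 42 = 51 |
| Day 90 to 120, 120 to 150, 150 to 180 | 30 each | 24 to 36 |

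**With haematology added at Day 60.** The 45-day gap splits into 60 − 45 = 15 days and 90 − 60 = 30 days. The longest on-treatment gap becomes 30 days (24 to 36), the same as the later monthly visits.

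**Subjects being titrated.** Titration needs at least 28 days of prior dosing, then steps of 300 mg every two weeks. The fastest path from 900 mg is therefore 1200 mg from Day 29 and 1500 mg from Day 29 + 14 = Day 43. A check two weeks after the last step falls on Day 57, leaving 90 − 57 = 33 days to the next scheduled test. That lies inside the 24 to 36 days of an ordinary monthly interval.

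**The case against.** The strongest reply is that Section 8.2.1 already covers the subjects at most risk. It does cover those whose dose is rising. A reader might infer that everyone in these groups goes untested for 45 days, including subjects newly on 1500 mg, a dose above those of which Section 5.3.1 says: "Doses of 1000 mg for 28 days and 900 mg for 90 days have been well tolerated". The documents do not support that. The two-weekly visits apply during escalation. Because the decision to escalate rests partly on haemoglobin and reticulocytes, the laboratory checks would naturally include them. What remains is a lack of precision: haematology is not named, and it is not clear that the visits continue after the last increase.

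A reader might also take the blood-volume table in Section 9.0 as proof that the dash is a slip. It allows "Haematology 2.0 Up to 10 20.0", and Table 5 yields nine haematology samples counting one pre-dose draw. But up to 10 is a ceiling that nine satisfies. By the same count HbA1c comes to 4 against 7 budgeted, carboxyhaemoglobin to 4 against up to 7, and NT-proBNP to 4 against up to 8. The printed volumes add to 265.9 mL against a stated total of 335.9 mL. The table is poor evidence of intent, and a dash among blank cells could equally mark a deliberate omission.

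Nor does Table 4 (Group 1) call for the same change. Day 60 there is the last dosing visit and also lacks biochemistry, so a haemoglobin result that day could hardly trigger a dosing stop.

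Other safeguards count for something. Restart requires haemoglobin below 12 g/dL and so a test. Footnote e and the notes to Table 3 allow extra sampling, weekly contact continues, and erythropoietin is measured at Day 60. But the extra samples depend on clinical indication or discretion, and a telephone call does not measure haemoglobin. The restart test says nothing about how soon haemoglobin is checked again afterwards.

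Finally, nothing in the plan requires haemoglobin at every visit or every 30 days.

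**Conclusion.** The point holds for subjects in Groups 2, 4 and 5 whose dose is constant or has been restarted at a reduced level. They have a 45-day interval (39 to 51) with no scheduled haemoglobin or reticulocyte result, half as long again as the next longest on-treatment interval in Table 5. The stop in Section 8.2 and the joint monitoring in Section 5.3 both rely on that schedule.

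The conclusion assumes that the dash means the test is not done, and that a site adds no discretionary samples. It does not depend on whether the omission was intended. A reader might infer that a subject is likely to cross 12.8 g/dL unseen. The documents do not support this, since they do not show how many subjects are near the threshold or how fast an individual's haemoglobin would rise during the interval. This is an inexpensive improvement to safety monitoring in a descriptive study of at most 16 subjects, and it does not call the study's validity into question.

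**What to change.** 1. In Table 5, replace the dash with an X for haematology at Day 60.
2. In Section 8.2.1, state that the two-weekly laboratory checks during titration include haematology and continue until two weeks after the last increase.
3. In Section 8.2, state that haemoglobin is rechecked two weeks after any restart at a reduced dose.

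The first change costs one 2.0 mL tube per subject at a visit where blood is already taken. It brings the scheduled haematology count from nine to ten, within the ceiling in Section 9.0. The other two may add an occasional sample after a dose change. No change to Table 4 is needed.

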8.2.1 Dose Titration

Provided the Principal Investigator determines that the 600mg dose (in Cohort 15), 900 mg dose (in Cohort 17), and 900 mg dose in the Cohorts 7, 11, 12, 14, 16 or 17 is well tolerated (after at least 28 days of dosing), and that the subject may receive further benefit from higher dosing (further improvement in haemoglobin, reticulocyte count or unconjugated bilirubin) the dose may be increased by one capsule (300 mg) every two weeks up to a maximum of 1500 mg dose.

When increasing the dose, the subject should return to clinical every 2 weeks for Laboratory and AE assessments

8.3 Dose Modification

Dose modification may be considered if warranted and as outlined below. All instances of study drug modification (change in dosing frequency, dose reduction or discontinuation) are to be captured in the subject research record and on the CRF and will require prompt notification of the medical monitor (i.e., typically within 48 hours). If the conditions/event leading to the dose modification have resolved, the original dose level and once a day dosing frequency should be resumed, unless in the judgement of the investigator, this cannot be done safely. Dose reductions will be made in 300 mg increments.

Dose level may be reduced for:

- Mild or moderate (Grade ≤ 2) adverse events that persist for ≥ 72 hours.
- Moderate (Grade ≥ 2) adverse events that require intervention (excluding over the counter symptomatic treatment such as acetaminophen, NSAIDs, antacids, antihistamines), that in the Investigator's judgement are deemed study drug related.
- Severe (Grade ≥ 3) adverse events that are not serious and that in the Investigator's judgement are deemed study drug related.

Study drug may be suspended for:

- Any AE that, in the opinion of the Investigator is drug related and warrants suspension of dosing.

- Re-initiation of dosing will be based on the Investigator's clinical assessment in consultation with the sponsor.
- If the conditions/event leading to the dose suspension have improved or resolved, dosing should be resumed at the original dose level and once a day dosing frequency, unless in the judgement of the investigator, this cannot be done safely.

Study drug may be discontinued for:

- Grade ≥ 3 drug-related SAE
- Any AE that, at the discretion of the Investigator, warrants discontinuation of study drug.

8.4 Warnings and Precautions

The preclinical data suggest an acceptable safety margin. The clinical data to date suggests that GBT440 is well tolerated. However GBT440 is in early clinical development. Facilities and staff for resuscitation and the treatment of other medical emergencies will be provided during clinic visits. During outpatient dosing periods, subjects will be provided with emergency numbers and contacted on a regular basis (weekly) by clinic staff to monitor their wellbeing.

